8.4.3 DEFINITION OF MTD

The MTDs will be defined as the highest dose of mRNA-2416 alone and in combination with durvalumab at which a DLT has been seen in less than 2 of 6 patients (<33%) during the first 28-days of study therapy.

If 2 or more adverse events that meet the definition of a DLT as defined in [Section 8.4.2](#), are observed beyond the first 28 days of study therapy within a dose escalation cohort, further enrollment may be held, pending safety analysis of the events by the SRC. These events will not affect the determination of the MTD but will be used in determining the appropriate RDE.

8.4.4 DOSE ESCALATION PROCEDURE

In order to be evaluable for dose determination, a patient must have received $\geq 50\%$ of the planned mRNA-2416 dose and $\geq 75\%$ of the planned durvalumab dose (Arm B) for Cycle 1 and must either have been followed ≥ 28 days following the first dose or have experienced a DLT within 28 days of the first dose. Patients who are not evaluable for dose determination may be replaced.

Dose escalation determination will not occur until the third patient in a cohort has completed their first 28-day study therapy.

- If no patient (0 of 3) in a dose cohort experiences a DLT during the first 28 days, then the next dose cohort of 3 patients will be enrolled at the next dose level per [Table 1](#) following consensus of the SRC.
- If 1 of 3 patients in a dose cohort experiences a DLT, an additional 3 patients will be enrolled in that dose cohort.
 - Provided that no more than 1 of 6 patients in the expanded dose cohort experiences a DLT within 28 days of the first dose, then a dose cohort of 3 patients will be enrolled at the next dose level per [Table 1](#) following consensus of the SRC.
- If ≥ 2 patients in a dose cohort experience a DLT within 28 days of the first dose, that cohort will have exceeded the MTD. No additional patients will be dosed at that level, and 3 patients will be enrolled in the preceding dose cohort, unless 6 patients have already been treated at that dose level. Using the same criteria, lower dose cohorts will be explored as the MTD until ≤ 1 of 6 patients experiences a DLT.

In the event that ≥ 2 of the first 6 DLT-evaluable patients in the 1.0 mg cohort experience a DLT, then the next cohort will be dosed with 0.5 mg mRNA-2416.

In the event that ≥ 2 of the first 6 DLT-evaluable patients in the 8.0 mg cohort experience a DLT, an intermediate dose cohort may be opened at 6.0 mg mRNA-2416.

9 **SELECTION OF PATIENTS**

9.1 **INCLUSION CRITERIA**

All patients must meet all of the following inclusion criteria:

1. Males or females ≥ 18 years of age who have provided written informed consent prior to completing any study-specific procedure
2. Disease state and prior therapies:
 - a. Dose Escalation and Dose Confirmation Periods: Histologically- or cytologically-confirmed advanced/metastatic solid tumor or lymphoma by pathology report and who has received, or been intolerant to, all approved therapies. Advanced solid tumors (i.e. including but not limited to melanoma, breast, head and neck squamous cell) and lymphomas (i.e. including by not limited to diffuse large B cell lymphoma) of any type are eligible for enrollment.
 - b. Dose Expansion Period: Histologically or cytologically confirmed diagnosis of: epithelial cancer of the ovary, fallopian tube, or peritoneum which is platinum resistant or platinum refractory. Patients must have received at least 2 prior lines of therapy. Patients with known BRCA mutation positive must have been treated with and progressed on at least 1 prior PARPi (poly(ADP-ribose) polymerase inhibitor)
3. No limit to the number of prior therapies
 - a. Patients who refuse standard treatments may also be considered provided that he/she has been made aware of all therapeutic options and it is documented in the study records.
4. Lesions for intratumoral injection and biopsies:
 - a. Dose Escalation: A minimum of one lesion that is easily accessible for injection where easily accessible is defined as a cutaneous or subcutaneous mass that is palpable and/or visualizable by ultrasound
 - b. Dose Confirmation: A minimum of one visceral lesion injectable with ultrasound or computer tomography (CT) guidance and that is not encasing or abutting major vascular structures or are in a location that are considered high risk for AEs by the enrolling physician
 - c. Dose Expansion: A minimum of one lesion amenable to injection (either non-visceral or visceral). Patients must have a tumor lesion amenable to biopsy and consent to a pre-treatment and an on-treatment biopsy. For patients with only one lesion amenable to injection, biopsy, and RECIST assessment, the lesion must be ≥ 2 cm.
 - d. Biopsy Cohort Enrichment: Patients must have a tumor lesion amenable to biopsy and consent to a pre-treatment and an on-treatment biopsy
5. All lesion(s) targeted for the initial injection must be ≥ 0.5 cm on longest diameter, be at least 5 mm thick, and have distinct borders based on exam or imaging, not close to critical structures such as major vessels, nerves, or airways
6. Patients must have measurable disease as determined by RECIST v1.1 (solid tumors) or Cheson 2014 criteria (lymphomas).

- a. Dose Expansion: Patients must have at least 1 measurable lesion per RECIST v1.1 which has not been previously irradiated.
7. Easter Cooperative Oncology Group (ECOG) performance status of ≤ 1
8. Adequate hematological and biological function, confirmed by the following laboratory values:
 - Bone marrow function
 - a. Absolute neutrophil count $\geq 1.5 \times 10^9/L$
 - b. Hemoglobin $\geq 9 \text{ g/dL}$ or $\geq 6.2 \text{ mmol/L}$
 - c. Platelets $\geq 100 \times 10^9/L$ without transfusion support
 - Hepatic function
 - d. Aspartate aminotransferase and alanine aminotransferase $\leq 2.5 \times$ upper limit of normal (ULN) ($\leq 5 \times$ ULN, if hepatic involvement of tumor)
 - e. Bilirubin $\leq 1.5 \times$ ULN ($< 3.0 \text{ mg/dL}$ if patient has Gilbert's disease)
 - Renal function
 - f. Serum creatinine $\leq 1.5 \times$ ULN or creatinine clearance of $> 50 \text{ mL/min}$ (using Cockcroft-Gault formula)
$$eCr[mL/min] = \frac{(140 - \text{Age [yrs]}) \times \text{Body Weight [kg]} \times [0.85 \text{ if Female}]}{72 \times \text{Serum Creatinine [mg/dL]}}$$
 - Coagulation function
 - g. Protime/international normalized ratio and activated partial thromboplastin time $\leq 1.5 \times$ ULN
 - Thyroid function
 - h. Thyroid-stimulating hormone within normal range.
9. Female patients of childbearing potential must have a negative serum pregnancy test during screening. Male and female patients must agree to use a highly reliable method of birth control (expected failure rate less than 1% per year) from the Screening visit through 120 days after the last dose of study drug. Patients must consent to following the contraception requirements in [Section 10.14.1](#) and [10.14.2](#).
10. Must have a life expectancy of at least 12 weeks
11. Body weight $> 30 \text{ kg}$

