10.4 DURVALUMAB DOSE MODIFICATION AND TOXICITY MANAGEMENT GUIDELINES

Dose delays are permitted for durvalumab (please see Appendix E for dose modification and toxicity management guidelines), however dose reductions are not permitted for durvalumab.

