10.5 Dose Omissions and Discontinuation of Study Drug Administration

Study treatment may be interrupted for situations other than treatment-related AEs such as medical and/or surgical events or logistical reasons not related to study treatment. Patients should be placed back on study

treatment within 3 weeks of the scheduled interruption, unless otherwise discussed with the Sponsor. The reason for interruption should be documented in the patient's study record.

Patients who have permanently discontinued study therapy will be scheduled for an End of Treatment visit within 14 days (± 2 days) of the decision to permanently discontinue study therapy and assessments will be performed per the Schedule of Events table ([Section 3](#)). Patients who have permanently discontinued study therapy should not be considered withdrawn from the study. They should return for the 30-day and 90-day safety follow-up visit from last dose and the tumor assessment follow-up visits per the Schedule of Events table. If the patient fails to return for these assessments for unknown reasons, every effort (e.g. telephone, email, letter) should be made to contact them.

The following are reasons for discontinuing study therapy without necessarily requiring withdrawal from the study:

- Patients who have completed 6 cycles of study therapy and have an overall tumor assessment of SD or better
- Patients who have experienced a Grade 4 treatment-related AE at any time during study treatment must discontinue from study treatment
- Patients who, in the opinion of the investigator, have incurred a Grade 3 drug-related DLT that has not recovered to Grade 1 or less within 14 days, or has recurred following restarting study therapy at a modified dose level.
- Patients who, in the opinion of the investigator, have incurred unacceptable toxicity that does not meet the pre-determined criteria for DLT (eg, late-onset, treatment-emergent toxicity after the DLT assessment window, or Grade 2 toxicities that are sufficiently durable or unresponsive to supportive intervention as to render them unacceptable in the opinion of the investigator) which has not recovered to Grade 1 or less within 28 days, or has recurred following restarting study therapy at a modified dose level.
- Patients who experience a Grade 3 hypersensitivity reaction or autoimmune events must discontinue from study treatment
- Patients who no longer have lesions that meet criteria for injection
- Pregnancy
- Physician's decision

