3.3. Treatment

Two investigational products, mRNA-2416 and durvalumab, are tested on patients with advanced relapsed/refractory solid tumor malignancies or lymphoma. mRNA-2416 is a novel mRNA encoding human OX40L encapsulated in a lipid nanoparticle, administered through repeated intratumoral injections on tumor lesions. Durvalumab in combination with mRNA-2416 in arm B is administered to study patients through intravenous infusion.

Arm A patients receiving treatment to superficial lesions will receive mRNA-2416 on Day 1 and Day 15 of a 28-day cycle for 6 cycles. Arm A patients receiving treatment to visceral lesions and all Arm B patients will receive mRNA-2416 on Day 1 and Day 15 for Cycle 1, and on Day 1 only for Cycles 2-6. All Arm B patients will receive durvalumab in combination with mRNA-2416 on Day 1 in each cycle. Dose levels of mRNA-2416 can be found in the protocol Table 1 and Table 2. In the event that ≥ 2 of the first 6 DLT-evaluable patients in the 8.0 mg cohort experience a DLT, an intermediate dose cohort may be opened at 6.0 mg mRNA-2416. Per protocol, the potential dose cohorts are 0.5 mg, 1.0 mg, 2.0 mg, 4.0

mg, 6.0 mg, and 8.0 mg of mRNA-2416 alone, and 2.0 mg, 4.0 mg, 6.0 mg, and 8.0 mg of mRNA-2416 in combination with durvalumab. Some cohorts may not have any patients enrolled during the course of the study. Only the dose cohorts that have patients enrolled will be analyzed. If the dose level of mRNA-2416 that a patient received at the first dose is different from the dose cohort that the patient was enrolled in, the patient may be analyzed in the dose level of mRNA-2416 that the patient received as specified in the analysis.

Following are the potential treatment arms and dose cohorts for Phase I and Phase II.

- Arm A
 - mRNA-2416 0.5 mg
 - mRNA-2416 1.0 mg
 - mRNA-2416 2.0 mg
 - mRNA-2416 4.0 mg
 - mRNA-2416 6.0 mg
 - mRNA-2416 8.0 mg
- Arm B
 - mRNA-2416 2.0 mg + Durvalumab
 - mRNA-2416 4.0 mg + Durvalumab
 - mRNA-2416 6.0 mg + Durvalumab
 - mRNA-2416 8.0 mg + Durvalumab

4. General Statistical Considerations

This document will provide details regarding the definition of analysis variables and analysis methodology to address all study objectives.

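### Protocol 8.4.4 applies the Cycle 1 exposure minimum even to a patient who has had a DLT, so a DLT that itself cuts Day 1 dosing short may drop out of dose determination (narrow, mainly Arm B)

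*Protocol*

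**What the plan says.** Protocol 8.4.4 sets two conditions for being evaluable for dose determination. The first is exposure in Cycle 1: at least 50% of planned mRNA-2416 and, in Arm B, at least 75% "of the planned durvalumab dose (Arm B) for Cycle 1 and must either have been followed" for 28 days. The second is that follow-up, with an alternative: "or have experienced a DLT within 28 days of the first dose. Patients who are not evaluable for dose determination may be replaced".

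The decision text counts differently. When two or more "patients in a dose cohort experience a DLT within 28 days of the first dose, that cohort will have exceeded the MTD", and no further patients are dosed at that level. Section 8.4.3 defines the MTD by DLTs in fewer than 2 of 6 patients. Neither refers to evaluability. Two later sentences in 8.4.4 do. One of them concerns two or more "of the first 6 DLT-evaluable patients in the 8.0 mg cohort experience a DLT", in which case a 6.0 mg cohort may be opened.

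Rules on stopping treatment bear on who can fall below the minimum:
- Protocol 10.5: "Patients who have experienced a Grade 4 treatment-related AE at any time during study treatment must discontinue from study treatment".
- Protocol 10.5: "Patients who experience a Grade 3 hypersensitivity reaction or autoimmune events must discontinue from study treatment".
- Protocol 10.4: "Dose delays are permitted for durvalumab".
- Protocol 10.7: an injection-related reaction of Grade 3 or above ends further mRNA-2416 injections. It does not mention durvalumab.
- Appendix E: a Grade 3 or 4 infusion-related reaction means permanent discontinuation.

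Section 8.2.4 runs Dose Confirmation by the rules of 8.4, and 8.2.7 takes evaluability for its DLT rate from 8.4.4.

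**The concern.** An exposure minimum exists to keep out patients who received too little drug to show whether the dose is tolerable. A patient who has already had a DLT has shown it. Because the two conditions are joined by *and*, such a patient must still pass the exposure test, and nothing in either document exempts them. The patients at risk of exclusion are those whose toxicity was abrupt enough to interrupt dosing, so their exclusion is informative.

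If the event is left out, the error has one direction. At 4.0 mg in Arm B it could support escalation. At 8.0 mg, the highest level in Protocol Table 2, it could support an MTD or RDE that should not have been cleared, with no higher cohort to reveal the mistake.

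**Working it through.** **1. Logic of the sentence.** Evaluable = exposure minimum AND (28 days of follow-up OR DLT). A DLT makes the bracket true but does nothing for the exposure term.

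**2. Who can fall below the minimum.**
- *Arm A.* Cycle 1 has two injections (Days 1 and 15; Protocol 8.2.1). One complete injection is 1/2 = 50%, which meets the threshold. A DLT that only prevents Day 15 therefore still counts; only an incomplete Day 1 injection fails.
- *Arm B.* Durvalumab is given on Day 1 of each cycle (SAP 3.3), so once in Cycle 1. The minimum is 0.75 × 1500 = 1125 mg, or 0.75 × 60 = 45 minutes of the standard one-hour infusion if the rate is constant (my assumption). Protocol 10.1 puts the injection first, with at least 30 minutes between the two.

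**3. Two routes in Arm B.**
- *Before the infusion.* A Grade 4 related event, or one classed as Grade 3 hypersensitivity, occurs after the injection. Section 10.5 ends study treatment, leaving durvalumab at 0%. For a reaction that is also injection-related, 10.7 stops only mRNA-2416, so 10.5 and 10.7 do not agree.
- *During the infusion.* A Grade 4 infusion reaction, or a Grade 3 one that qualifies as a DLT, stops the infusion before 1125 mg.

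The Grade 4 cases are DLTs outright. The Grade 3 cases depend on 8.4.2: its Arm B table makes a Grade 3 infusion reaction a DLT only if unresolved within 6 hours, while the bullet below the table takes in any related Grade 3 event apart from vitiligo or alopecia.

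**4. Effect on a decision.** Two DLTs in six patients is 2/6 = 33.3%, above the MTD limit. If one is excluded and the replacement has no DLT, the count is 1/6 = 16.7%, and the dose passes.

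**5. Illustrative size.** The documents give neither the true DLT rate *t* nor the share *f* of DLTs that fall below the minimum; both are assumed. If every such patient is excluded and replaced, the DLT rate among counted patients is p = t(1 − f)/(1 − tf). Under a standard 3+3, P(clear) = (1 − p)³ + 3p(1 − p)⁵.

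| t | f | p | P(clear) |
|---|---|---|---|
| 40% | 0 | 0.4000 | 30.9% |
| 40% | 5% | 0.38/0.98 = 0.3878 | 33.0% |
| 40% | 10% | 0.36/0.96 = 0.3750 | 35.1% |
| 30% | 0 | 0.3000 | 49.4% |
| 30% | 5% | 0.285/0.985 = 0.2893 | 51.6% |
| 30% | 10% | 0.27/0.97 = 0.2784 | 53.9% |

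The rise is about 2 percentage points at f = 5% and 4 to 5 at f = 10%.

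**6. Section 8.2.7.** Its numerator is all patients with a DLT at the dose; its denominator is evaluable patients only. Suppose three patients have DLTs, one of them under-exposed, and nine are evaluable. The ratio is 3/9 = 33.3%, which meets the 33% suspension trigger. If the under-exposed patient becomes evaluable it is 3/10 = 30.0%, which does not.

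**The case against.** The best defence is that the operative text is mandatory and replacement is only permitted. With two DLTs in a cohort, the bullet closes it, and a permissive clause should not displace that. Escalation also needs consensus of the safety review committee (SRC), which sees all available safety data. This largely stands: on the bullets' own wording both DLTs count, and a reader who infers that the plan certainly discards such events goes too far. What remains is a conflict. The evaluability sentence governs dose determination, the bullets do not say they override it, and 8.4.1 makes the 8.4.4 guidelines a basis for all SRC decisions.

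A second defence is that an Arm B patient who received no durvalumab says little about the combination. That is a fair cost of the fix. Against it, durvalumab is fixed at 1500 mg in every row of Table 2, so the component being escalated is the one the patient received.

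Three stronger readings are not supported:
- That the 8.0 mg sentence is a clearance rule on evaluable patients. SAP 3.3 repeats it and lists "and 2.0 mg, 4.0 mg, 6.0 mg, and 8.0 mg of mRNA-2416 in combination with durvalumab", so it reaches Arm B. But it says only when a 6.0 mg cohort may open; clearance rests on the bullets and 8.4.3.
- That any Grade 3 injection reaction removes the Cycle 1 infusion. Section 10.7 stops only mRNA-2416, and 10.4 allows durvalumab to be delayed.
- That Arm A is equally exposed. A complete Day 1 injection already meets the 50% minimum.

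**Conclusion.** The point holds in narrow form and should be fixed. As written, the evaluability sentence can exclude a DLT that itself cut Day 1 dosing short, and it conflicts with the 3+3 bullets and 8.4.3. It matters mainly in Arm B, and most clearly for Grade 4 reactions, which do not depend on how the Grade 3 wording in 8.4.2 is resolved.

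The direction is certain: an omission can only favour clearing the dose. The size is not. The 2 to 5 points are upper bounds for the assumed t and f, because they take every under-exposed DLT as excluded and replaced, whereas replacement is optional. In a single cohort, though, one such patient can decide between 2 of 6 and 1 of 6.

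**What to change.** In Protocol 8.4.4, define the DLT-evaluable set so that the exposure and 28-day minimums apply only to patients without a DLT, and any treated patient with a DLT within 28 days of the first dose is counted. Use that set by name in the 3+3 bullets and in 8.4.3. This needs no new data. The cost is that a DLT after little drug, or in Arm B without durvalumab, counts fully against the dose level, which is the cautious direction for dose determination.

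The change is not confined to 8.4.4. Because 8.2.7 takes its evaluability from there, these patients would also enter its denominator, and the computed rate can fall, as in the 3/9 to 3/10 example. The sponsor must reconcile 8.2.7 with 8.4.4 in the same amendment and tell the SRC.

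Three related inconsistencies also need reconciling: 10.5 with 10.7 on reactions after the injection; the Arm B table in 8.4.2 with the bullet below it; and SAP 9.1.1, which lists only the Arm A DLT criteria although its table is sorted on the Arm B total. The last two are separate points.

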--	--

	
a. Absolute neutrophil count $\geq 1.5 \times 10^9/L$b. Hemoglobin $\geq 9 \text{ g/dL}$ or $\geq 6.2 \text{ mmol/L}$c. Platelets $\geq 100 \times 10^9/L$ without transfusion support 
Hepatic function
 
d. Aspartate aminotransferase and alanine aminotransferase $\leq 2.5 \times$ upper limit of normal (ULN) ($\leq 5 \times$ ULN, if hepatic involvement of tumor)e. Bilirubin $\leq 1.5 \times$ ULN ($< 3.0 \text{ mg/dL}$ if patient has Gilbert's disease) 
Renal function
 
f. Serum creatinine $\leq 1.5 \times$ ULN or creatinine clearance of $> 50 \text{ mL/min}$ (using Cockcroft-Gault formula) $eC_{Cr}[\text{mL/min}] = \frac{(140 - \text{Age [yrs]}) \times \text{Body Weight [kg]} \times [0.85 \text{ if Female}]}{72 \times \text{Serum Creatinine [mg/dL]}}$ 
Coagulation function
 
g. Protime/international normalized ratio and activated partial thromboplastin time $\leq 1.5 \times$ ULN 
Thyroid function
 
h. Thyroid-stimulating hormone within normal range 
9. Female patients of childbearing potential must have a negative serum pregnancy test during screening. Male and female patients must agree to use a highly reliable method of birth control (expected failure rate less than 1% per year) from the Screening visit through 120 days after the last dose of study drug. Patients must consent to following the contraception requirements in Section 10.14.1 and 10.14.2
 
10. Must have a life expectancy of at least 12 weeks
 
11. Body weight $> 30 \text{ kg}$.

--	---

Exclusion Criteria

Any of the following criteria will exclude patients from study participation:

1. Active central nervous system tumors or metastases
2. Treatment with chemotherapy, radiation (local radiation for palliative care is permitted), hormonal anti-cancer treatment, or biologic therapy < 14 days prior to the first day of study treatment (Cycle 1 Day 1 [C1D1])
 - a. Treatment with any other investigational agent or treatment with any anti-cancer monoclonal antibody, immunostimulant, or vaccine < 28 days prior to C1D1.
3. Any unresolved toxicity NCI CTCAE Grade ≥ 2 from previous anticancer therapy with the exception of alopecia, vitiligo, and the laboratory values defined in the inclusion criteria

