10.14.1 INSTRUCTIONS FOR MALE PATIENTS

Non-sterilized male patients who are not abstinent and intend to be sexually active with a female partner of childbearing potential must use a male condom plus spermicide from the time of screening throughout the total duration of the drug treatment and the drug washout period (90 days after the last dose of study treatment). Periodic abstinence, the rhythm method, and the withdrawal method are not acceptable methods of contraception. Male patients should refrain from sperm donation throughout this period.

Female partners (of childbearing potential) of male patients must also use a highly effective method of contraception throughout this period (Table 5).

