10.14.2 INSTRUCTIONS FOR FEMALE PATIENTS

Female patients of childbearing potential who are not abstinent and intend to be sexually active with a non-sterilized male partner must use at least 1 highly effective method of contraception (Table 5) from the time of screening throughout the total duration of the drug treatment and the drug washout period (90 days after the last dose of durvalumab monotherapy). Non-sterilized male partners of a female patient of childbearing potential must use a male condom plus spermicide throughout this period. Cessation of birth control after this point should be discussed with a responsible physician. Periodic abstinence, the rhythm method, and the withdrawal method are not acceptable methods of contraception. Female patients should refrain from breastfeeding throughout this period.

Please note, females of childbearing potential are defined as those who are not surgically sterile (ie, bilateral salpingectomy, bilateral oophorectomy, or complete hysterectomy) or post-menopausal.

Women will be considered post-menopausal if they have been amenorrheic for 12 months without an alternative medical cause. The following age-specific requirements apply:

- Women <50 years of age would be considered post-menopausal if they have been amenorrheic for 12 months or more following cessation of exogenous hormonal treatments and if they have luteinizing hormone and follicle-stimulating hormone levels in the post-menopausal range for the institution.
- Women ≥50 years of age would be considered post-menopausal if they have been amenorrheic for 12 months or more following cessation of all exogenous hormonal treatments, had radiation-induced menopause with last menses >1 year ago, had chemotherapy-induced menopause with last menses >1 year ago.
- Women who are surgically sterile (ie, bilateral salpingectomy, bilateral oophorectomy, or complete hysterectomy) are eligible.

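### The protocol sets two post-treatment contraception periods (120 and 90 days), and the 90 days for women run from a durvalumab monotherapy dose that many of them never receive

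*Protocol*

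**What the plan says.** Inclusion criterion 9 appears in the Section 2 summary and in Section 9.1. It covers both sexes, demands a method with an expected failure rate under 1% per year, and runs "from the Screening visit through 120 days after the last dose of study drug". It then adds: "Patients must consent to following the contraception requirements in Section 10.14.1 and 10.14.2".

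Section 10.14.1 (men) has non-sterilized men use a condom plus spermicide from screening through treatment and the "drug washout period (90 days after the last dose of study treatment"). It adds two further duties: "Male patients should refrain from sperm donation throughout this period", and female partners "must also use a highly effective method of contraception throughout this period (Table 5").

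Section 10.14.2 (women) requires a highly effective method over the same kind of period, but its washout is defined as "90 days after the last dose of durvalumab monotherapy". It also adds two duties: "Non-sterilized male partners of a female patient of childbearing potential must use a male condom plus spermicide throughout this period" and "Female patients should refrain from breastfeeding throughout this period". It says that stopping birth control after that point should be talked over with a physician.

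Section 8.3 gives Arm A mRNA-2416 only, for 6 cycles. In Arm B, single-agent durvalumab is optional and follows completion of 6 combination cycles.

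**The concern.** One eligibility item imposes two end dates on the same patient, and nothing says which governs. The female rule also counts from an event that does not occur for a whole arm and for part of the other.

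This is a matter of participant protection and protocol consistency. Section 10.14 states that nothing is known about the effects of the study medication on the human fetus. Section 6.2 reports a weakly positive rat micronucleus result for mRNA-2416, though the sponsor judged the risk to patients low. A site that works from Section 10.14 would release men 30 days before criterion 9 does, and could not set an end date for two of the rules that apply to Arm A women. The last scheduled pregnancy test is at the 90-day safety visit (Section 3), so the disputed 30 days fall after it and the written instruction is the main safeguard.

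**Working it through.** The plan gives no computed figure to reproduce. The check sets the current sections side by side and counts study days.

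**Inputs**
- Criterion 9: 120 days from the last dose of study drug, both sexes (Sections 2 and 9.1).
- Section 10.14.1: 90 days from the last dose of study treatment, men.
- Section 10.14.2: 90 days from the last dose of durvalumab monotherapy, women, with no separate rule by arm.
- Cycle length: 28 days. mRNA-2416 is given up to Cycle 6 Day 15 (Arm A, superficial lesions) or Cycle 6 Day 1 (Arm B, and Arm A visceral lesions) (Sections 8.2.3 and 10.1).
- Single-agent durvalumab: Arm B only, optional, after 6 combination cycles (Section 8.3).

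**Gap where both rules can be computed:** 120 − 90 = 30 days. This holds for men in both arms. It also holds for Arm B women on single-agent durvalumab, because their last monotherapy dose is also their last dose of any study drug.

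**Illustrative end dates.** The study day of Cycle c Day d is (c − 1) × 28 + d.

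| Patient | Last dose | Criterion 9 | Section 10.14 |
|---|---|---|---|
| Arm A man, superficial lesion, last dose Cycle 6 Day 15 | 5 × 28 + 15 = 155 | 155 + 120 = 275 | 155 + 90 = 245 |
| Arm A woman, same schedule | 155 | 275 | none: no durvalumab given |
| Arm B woman, last dose Cycle 6 Day 1, does not continue | 5 × 28 + 1 = 141 | 141 + 120 = 261 | none: no monotherapy dose |
| Arm B woman, one single-agent dose 28 days later | 141 + 28 = 169 | 169 + 120 = 289 | 169 + 90 = 259 |

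**What criterion 9 does and does not rescue.** It fixes a 120-day end for the patient's own birth control. It is silent on four further duties found only in Section 10.14: partner condom plus spermicide and no breastfeeding (women), and no sperm donation and contraception by the female partner (men). These last only for the period that each subsection defines. The two male duties therefore end at 90 days. For the women in rows 2 and 3 of the table, the two female duties have no end date.

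**Cross-reference.** Section 10.14.1 and the opening paragraph of Section 10.14.2 cite Table 5 for contraceptive methods. Table 5 lists supportive medications; the methods are in Table 10, which Section 10.14.2 cites correctly further down.

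**The case against.** The best reply is that the two rules can be satisfied together. Criterion 9 is conjunctive, nothing in Section 10.14 releases a patient from it, and anyone who keeps to 120 days meets both. For the patient's own birth control this stands. It does not supply the missing anchor in Section 10.14.2, and it does not reach duties that criterion 9 never mentions.

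A second reply is that the sperm-donation and female-partner rules have a single clear end at 90 days, so they do not strictly conflict with criterion 9, and no section shows 90 days to be inadequate for them. That is fair as far as the wording goes. But Section 10.14.2 says condoms, with or without spermicide, are not highly effective, and Table 10 lists only intrauterine and hormonal methods. For a sexually active, non-sterilized man with a partner of childbearing potential, the under-1% standard in criterion 9 is therefore met in practice through her method, and the instruction covering her stops at day 90.

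The man's own condom-plus-spermicide rule is also specific to Section 10.14.1 and could be counted as a fifth duty. That changes the tally, not the conclusion.

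The practical reach is limited. A sensible reader would start the washout at the end of treatment. The partner-condom rule concerns only women of childbearing potential, and breastfeeding women are excluded at entry (exclusion 17). The documents do not say how many women are affected, and the consent form was not available for review, so what patients were told is unknown. These points limit the severity, but the text is still wrong as written.

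**Conclusion.** The concern holds, and the conflict lies in the current sections of the protocol. Criterion 9 and Section 10.14 differ by 30 days for men in both arms and for Arm B women who receive single-agent durvalumab. For Arm A women, and for Arm B women who stop before that phase, the Section 10.14.2 period cannot be computed, so two of the four additional duties have no end date.

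The conclusion rests on reading durvalumab monotherapy as the single-agent phase described in Section 8.3. If it meant any durvalumab dose, Arm B women would have an anchor but Arm A women still would not, and the 90 against 120 days would remain.

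The change should be made, with high confidence. No endpoint, sample size or decision rule depends on it.

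**What to change.** In Sections 10.14.1 and 10.14.2, define the washout as 120 days after the last dose of any study drug (mRNA-2416 or durvalumab, whichever is later). This matches the stricter rule that patients already accept at enrolment, and the anchor exists in both arms. If the sponsor can justify 90 days, change criterion 9 in Sections 2 and 9.1 to 90 days from that same anchor, and use the anchor in both subsections.

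Change the Table 5 references in Sections 10.14.1 and 10.14.2 to Table 10. Check the consent form and align it if it carries the same conflict.

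The cost is wording. Under the 120-day option, the partner, sperm-donation and breastfeeding restrictions last up to 30 days longer.
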